GEHC	General Electric Healthcare
ICF	Informed Consent Form
ISO	International Standards Organization
MWS	GE MyWorkshop Internal Documentation System
PRTS	Protocol synopsis
SADE	Serious Adverse Device Effect
SAE	Serious Adverse Event
SPR	System Problem Report
US	United States
U/S	Ultrasound
USADE	Unexpected Serious Adverse Device Effect

STUDY SYNOPSIS	
Sponsor:	General Electric Company, acting through its GE Healthcare Business
Research Type:	This is a clinical, open label, non-randomized, prospective, single-site, non-blinded research study, that will enroll from the accessible women (aged >18 years) in the 2nd and 3rd trimesters of pregnancy. The study will be conducted in two parts, including an initial pilot for determination of parameters (Part 1) and continued testing (Part 2).
Regulatory Status:	This is a pre-market research study of the following products: Pre-market: Vscan Access R2 Ultrasound System Post-market: GE Corometrics* 170 Series Fetal Monitor
Background and Rationale:	Fetal heart rate (FHR) estimation is an important tool for assessment of fetal well-being and development during pregnancy that is traditionally measured using M-mode or Doppler methods on ultrasound systems. The Vscan Access Ultrasound system is a diagnostic ultrasound imaging system manufactured by the study Sponsor, GE Healthcare (GEHC) and equipped with Assisted FHR, a novel investigational feature that enables visualization and measurement of fetal heart rate. This feature visually maps obstetrical and abdominal anatomical structures and fluid and is intended to be used by qualified and trained primary and specialty health care professionals, including midwives, other paraprofessionals and general physicians. The built-in preset workflows and protocols, particularly enable novice users to scan efficiently and conduct basic screening exams. This technology provides an innovative way of assessing FHR that is semi-automated and does not involve any manual measurements once the fetal heart is scanned. This study is being conducted to validate procedural accuracy of the Vscan Access R2 Ultrasound System with Assisted FHR Measurement in users of all experience levels.


Procedures/ Methods:
	
Subjects in the initial pilot period (Part 1) and validation testing (Part 2) will undergo up to 45 minutes of ultrasound scanning, including up to 8 test scans on the Vscan Access R2 Ultrasound System with Assisted FHR (research device) and a conventional commercially available ultrasound device. Subjects will also undergo routine commercially available noninvasive FHR monitoring as a reference. All procedures will be conducted at a Sponsor, GE Healthcare (GEHC), facility. All members of the study staff will be qualified based on experience and trained prior to participation.
 
The study population will consist of asymptomatic women ages 18 or older in the second (2nd) and third (3rd) trimesters of pregnancy. Users will be instructed to use the VScan Access R2 device to take a 3 second video of the volunteer, which will result in a calculated fetal heart rate measurement from the monitor. Volunteers will also undergo routine commercially available FHR monitoring using the current standard of care.
 
The first session (Part 1) will be a run-in session, in which the parameters and procedures will be a replica of the study but these results will not count towards the documented results. There will be four (4) sessions following this run-in session (Part 2). Each of these sessions will be approximately 3-4 hours in length over a period of 1-2 weeks.
 
In each session, there will be 1-2 users and 3 volunteers. The users will be instructed to take as many measurements as possible during the allotted time. Finalization of the procedure to calculate accuracy is to be determined based on the run-in procedures executed in Part 1. The specific procedures for the measurement of accuracy which will be used for validation will be performed by the team during Part 1 of the study.

Objectives:
	
Data from Part 1 and Part 2 may be pooled or analyzed as separate subgroups, as determined necessary by the sponsor.
 
The primary objective is to validate the accuracy of the VScan Access R2 ultrasound assisted FHR measurement compared to the reference standard in a pregnant population.
 
The exploratory objective is to collect usability data for further user experience optimization.
 
The safety objective is to collect safety information, including type and number of AEs, SAEs, and other device issues.


Endpoints:
	
The primary endpoint is FHR data from the investigational and comparator devices on a per-sample basis in bpm (beats per minute).
 
The exploratory endpoint is the number of subject cases containing scan parameters will be reported and descriptively summarized as necessary to assist in evaluation of usability of the Vscan Access R2 Ultrasound System.
 
The safety endpoint is the type and number of AEs, SAEs, and device issues.

Eligibility criteria:
	
Inclusion criteria: All included subjects will be:
 
 1. Women aged 18 years or older at the time of consent; 2. By self-report, are in the 2nd or 3rd trimester of pregnancy; 
AND
 
 3. Able and willing to provide written informed consent for participation. 	
Exclusion criteria: Subjects will be excluded that:
 
 1. Are direct employees/contractors of General Electric (GE); 2. Have anatomical characteristics or comorbid medical conditions that prevent completion of ultrasound scanning using the study device; 
OR
 
 3. Are potentially put at additional risk by participating, in the opinion of study staff.

Sample size and Sites:
	
Up to 25 subjects will be included as part of this study to achieve the targeted number of complete and evaluable subjects. The target sample size for this study is 15 subjects. This includes testing up to 5 subjects in Part 1 and 20 subjects in Part 2 of the study. The sample size for both study parts is based on estimation necessary for study device evaluation and validation requirements. This study is not statistically powered for any measure.
	

Study duration:
	
The study is expected to last approximately 6 weeks. Estimated start date: 01/Sep/2017 Estimated end date: 30/Oct/2017
	

ADMINISTRATIVE STRUCTURE OF INVESTIGATION		
Clinical Affairs Project Manager (Sponsor Contact):	[name] Tel: [name] e-mail: [contact]	GE Healthcare (GEHC) Address: [name]
Research Manager:	[name] Tel: [name] e-mail: [contact]	GEHC Address: [name]
Medical Monitor:	[name], DNB, MBBS Tel: [name] e-mail: [contact]	GEHC Address: [name]

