1. BACKGROUND AND JUSTIFICATION

FHR estimation is an important tool for assessment of fetal well-being and development during pregnancy that is traditionally measured using M-mode or Doppler methods on ultrasound systems or with conventional acoustic systems. The Vscan Access R2 Assisted FHR method is an innovative way of assessing FHR that is semi-automated and does not involve any manual measurements once fetal heart is scanned. Assisted FHR method may have clinical benefits, such as improved ease of training and utilization in real clinical cases.

FHR monitoring is important for prenatal care and can be used to indicate a variety of clinically relevant conditions in the mother and fetus, which is the subject of extensive research collaborations worldwide.¹ Training clinicians to perform accurate FHR measurements can be challenging due to various discrepancies in both practice and the acceptable standards for routine FHR measurement.

FHR measurement is important to clinical practice and widely considered safe and effective. A study by Ruma et al.² found that appropriate maternal-fetal care, including FHR determination via obstetric ultrasound improves the outcomes of mothers and their infants, in part due to improved accuracy using advanced ultrasound techniques. This has been demonstrated in large clinical trials, including the Eurofetus study which examined second trimester ultrasounds prospectively.³ American Institute of Ultrasound in Medicine (AIUM) recommends medically necessary fetal ultrasound in the 2nd and 3rd trimester, which are widely considered to be safe for mother and fetus.^{4,5}

The Vscan Access R2 Ultrasound System with its Assisted FHR feature has the potential to improve the accuracy and reproducibility assessment of FHRs for second and third trimester scans, and it also may reduce the variability between clinicians performing similar procedures. Results from this study may be useful for the evaluation of procedural accuracy of the Vscan Access R2 Ultrasound System with Assisted FHR compared to the conventional methods of measuring FHR on ultrasound or Doppler devices.

Justification for Use of GE-Operated Facility

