5.7 Subject Procedure

Subjects will be asked basic demographic and pregnancy status questions. Subjects will be screened for eligibility and no other preparations are required to participate. Following consent, eligible subjects will be fitted with a conventional FHR Monitor while simultaneously undergoing a non-invasive abdominal ultrasound scan using the Vscan Access R2 system with Assisted FHR and a commercially available ultrasound device (reference standard). FHRs will be collected using both devices.

Eight (8) paired ultrasound scans with FHR Monitor determination will be attempted for each subject participating in the study (a total of 16 scans each, 8 with the research device and 8 with the reference device). Each paired scan will last approximately 5 minutes for both determinations, for a total of approximately 40 minutes of total ultrasound exposure. Breaks may be provided between scans based on operator availability or requests by the subject. At least 2 operators will perform scanning for each subject.

A prospective blocked schedule detailing the order in which scanning will be conducted for each operator and subject will be prepared before the start of subject scanning.

Up to 5 clinicians (Experienced sonographers, Novice users e.g. newly qualified sonographers, nurses/midwives, etc.) - with an approximate 80-20 split of novice vs. experienced - with respect to ultrasound familiarity & scanning experience will be aspired for.

The resultant ultrasound and case data (including basic demographics; self-reported pregnancy status; and information about when and how the ultrasound exam was conducted) will be collected for each subject.

All procedures will be conducted at a Sponsor, GE Healthcare (GEHC), facility. All members of the study staff will be qualified based on experience and trained prior to participation.

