6. STUDY DATA COLLECTION AND ASSESSMENTS

6.6 Primary Assessment

The operator will record FHR values estimated from the reference and research ultrasound devices to the CRF. Relevant demographics and clinical information will also be recorded to the CRF.

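### Three fetal heart rate methods are applied to each woman, but the plan provides for recording two values per pair, so the monitor is not put to use as a common yardstick

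*Combined protocol and SAP*

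**What the plan says.** **Methods applied.** The synopsis (Procedures/Methods) describes "up to 8 test scans on the Vscan Access R2 Ultrasound System with Assisted FHR (research device) and a conventional commercially available ultrasound device", and then adds: "Subjects will also undergo routine commercially available noninvasive FHR monitoring as a reference". Section 5.7 has the woman "fitted with a conventional FHR Monitor while simultaneously undergoing a non-invasive abdominal ultrasound scan" with the Vscan and the commercial device. On a plain reading that is three methods.

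**Values kept.** Section 5.7 continues: "a commercially available ultrasound device (reference standard). FHRs will be collected using both devices". It counts 16 scans per woman, 8 research and 8 reference, at about 5 minutes per pair. It also mentions a monitor determination with each pair. Section 6.6 sends two values to the CRF: "The operator will record FHR values estimated from the reference and research ultrasound devices to the CRF". Section 6.7 lists further CRF items, and a monitor FHR is not among them.

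**Reference.** The sections conflict:
- Synopsis: FHR monitoring.
- Section 2.3: the monitor and M-mode ultrasound, merged into one phrase.
- Sections 3.1 and 3.3: the Corometrics 170 monitor (in 3.1, as an example).
- Section 5.7: the commercial ultrasound device.
- Section 6.6: wording that implies an ultrasound device.

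**Purpose and analysis.** Section 1 says the device "has the potential to improve the accuracy and reproducibility assessment of FHRs for second and third trimester scans", and that results may help evaluate its accuracy "compared to the conventional methods of measuring FHR on ultrasound or Doppler devices". The primary objective (3.1.1) is accuracy against the reference standard. Sections 10.6 and 10.8 plan no hypothesis test, only descriptive tables and listings.

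**The concern.** A difference between two imperfect methods does not say which one was off. Its variance is the sum of both error variances plus the variance of any true change in FHR between the readings. Its mean is one bias minus the other. A reader who takes the whole spread as Vscan inaccuracy charges the Vscan with the other method's error and with real fetal variation.

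A third method is already worn during scanning. If its value is captured beside each reading, the true change drops out of each monitor-based difference, and conventional ultrasound gets its own agreement figure for comparison. If the value is not captured, it may not be recoverable later.

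What is at stake is how the accuracy result can be interpreted, and whether the data can support any later statement about the Vscan relative to conventional ultrasound.

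**Working it through.** **1. The plan's own count.** 8 pairs × 2 devices = 16 scans, and 8 × 5 min = 40 min. Both match section 5.7. The plan states no alpha, power, margin or SD, so there is no sample-size figure to reproduce. Every SD below is an assumption.

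**2. What the difference contains.** Write V for the Vscan, R for the reference, C for the monitor, s for an error SD and d for the SD of true FHR change between the two readings. With independent errors:
- Var(V − R) = sV² + sR² + d²
- mean(V − R) = biasV − biasR

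**3. Different truths, same difference.**
- Error SDs (V, R) of (1, 4.9), (3.54, 3.54) and (4.9, 1) bpm all give SD(V − R) = 5.0.
- Biases (V, R) of (+3, 0), (0, −3) and (+1.5, −1.5) bpm all give a mean difference of +3.

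**4. Size when commercial ultrasound is the reference.** Take error SDs of 2 and 4 bpm, in either order.
- d = 0: √(4 + 16) = 4.47; limits 1.96 × 4.47 = ±8.8 bpm.
- d = 3: √(4 + 16 + 9) = 5.39; limits ±10.6 bpm.

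The step from ±8.8 to ±10.6 is fetal variation, not device error.

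**5. What the monitor adds.** Assume a monitor error SD of 2 bpm, independent of the ultrasound errors, with each value aligned in time to its ultrasound reading.

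| Assumed SDs | SD(Vscan − monitor) | SD(ultrasound − monitor) |
|---|---|---|
| Vscan 2, ultrasound 4 | √(4 + 4) = 2.83 | √(16 + 4) = 4.47 |
| Vscan 4, ultrasound 2 | 4.47 | 2.83 |

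The two cases now separate, and d does not enter. Monitor error does: in the first row the Vscan SD shows as 2.83 rather than 2, a factor of 1.41.

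**6. What the replicates already offer.** Eight readings per device per woman carry information on random error through their within-woman spread. This was simulated with 15 women × 8 pairs and error SDs of 2 and 4 bpm, asking how often the device with the larger error shows the larger spread.

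| Assumed within-woman FHR SD | No change between readings | 3 bpm change, equal FHR spread at both readings |
|---|---|---|
| 2 bpm | about 100% | about 100% |
| 5 bpm | about 99% | about 98% |
| 10 bpm | about 91% | about 87% |

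This breaks down if the added FHR variation falls on one device's readings only. With equal true errors of 3 bpm, a within-woman FHR SD of 5 bpm and an extra 4 bpm on the reference readings alone, the reference looks worse in about 99% of runs.

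**7. If the monitor is the reference.** Vscan minus monitor is then already the primary comparison. What is missing is commercial ultrasound minus monitor.

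**The case against.** **The CRF may hold a third value.** Section 5.7 foresees a monitor determination with each pair, the endpoint in 3.2.1 speaks of comparator devices, and the CRF is not in the documents. This stands. A reader might infer that only two values are recorded; the documents support only that no section provides for recording or analysing a third.

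**The root is the naming of the reference.** Sections 3.1, 3.3 and 4.1 set the Vscan against the Corometrics monitor, the synopsis product list names only those two devices, and section 1.2 puts all study ultrasound exams on the Vscan. On that reading the main comparison is already against the monitor. This stands in part. Naming one reference would settle which two values are compared, but it would not add the third.

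**The planned data are not blind to which device is noisier.** A reader might infer that two values per pair cannot separate two opposite truths. For random error that is false, as step 6 shows. It holds for each single difference and for bias. With three methods, too, bias is relative unless one is taken as truth. The plan contains no replicate-based analysis.

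**Superiority is not a study question.** This stands. Section 1 states a potential, not an expectation, and its remark about discrepancies concerns practice and standards in training clinicians. It is not a finding that conventional readings are wrong.

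**The plan never says the whole difference is Vscan error.** True: section 10.8 is descriptive only, and the synopsis leaves the accuracy procedure to Part 1. That makes this a gap to fill before Part 2 rather than an error in a stated analysis.

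**Conclusion.** The point holds in a limited form. Three methods are applied, two recorded values are provided for, and the monitor value has no stated recording rule, time-matching or analysis. The sections naming the reference conflict and must be reconciled.

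If commercial ultrasound is the reference, the reported difference combines both devices' errors with true FHR change, and the relative bias cannot be attributed to either device. Under the assumed SDs of 2 and 4 bpm the limits are about ±8.8 bpm, or about ±10.6 bpm with a 3 bpm true change. If the monitor is the reference, only the conventional-ultrasound benchmark is missing.

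A reader might conclude that the study fails its primary objective. The documents do not support that: the objective is accuracy against the reference standard, no hypothesis is tested, and better accuracy than conventional ultrasound is only a stated potential. The consequence is a limit on what can be claimed. The sizes rest on assumed SDs, independent errors and, for the monitor-based figures, good time alignment.

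**What to change.** 1. Reconcile the synopsis and sections 2.3, 3.1, 3.3, 5.7 and 6.6 so that one device is named as the reference, and state which values go on the CRF.
2. In 6.6, record the time-matched monitor FHR beside each Vscan reading and beside each commercial-ultrasound reading.
3. In 10.8, report Vscan minus monitor and commercial ultrasound minus monitor, each with mean, SD and 95% limits. Add the difference in bias and the ratio of SDs between the two, with intervals that resample women because readings cluster within a woman. Keep the named primary comparison.
4. State that each difference still contains monitor error, and that the comparison assumes this error is independent of the ultrasound errors and that readings are aligned in time.

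Cost: no added scanning, because the monitor is already worn. There are 8 × 2 = 16 extra CRF entries per woman, which is 240 for 15 women or 320 for 20 (Table 1 and section 10.7 give different Part 2 numbers), plus a few table rows. The CRF should be settled before Part 2 starts.

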3.3 Summary of Study Design

This is a Clinical, pre-market open label, non-randomized, prospective, single-site, non-blinded, research study, that will enroll from the accessible adult (aged >18 years) female population in the 2nd and 3rd trimesters of pregnancy. The study will be conducted in two stages, beginning with a run-in study (Part 1), followed by a clinical study (Part 2). The results of the run-in pilot study will not be included in the results and data analysis; rather, Part 1 of this study will be used to test procedures and determine any experimental factors that have yet to be defined. The study will be conducted at a GE-operated facility. The study is expected to last approximately 6 weeks. The study is not statistically powered for any measure, and is intended to evaluate procedural accuracy of the Vscan Access R2 Ultrasound System Assisted FHR versus use of a conventional FHR monitor (reference): GE Corometrics* 170 Series Fetal Monitor.

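### Nothing fixes the Vscan reading before the reference can be seen, or requires repeats and failures to be logged, so selective repeats could flatter the per-sample accuracy

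*Combined protocol and SAP*

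**What the plan says.** The primary objective is to validate accuracy (Section 3.1.1), using FHR in bpm per sample from both devices (Section 3.2.1).

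- **Amount of scanning.** The synopsis (Procedures/Methods) allows "up to 45 minutes of ultrasound scanning, including up to 8 test scans on the Vscan Access R2 Ultrasound System with Assisted FHR". Section 5.7 states "Eight (8) paired ultrasound scans with FHR Monitor determination will be attempted for each subject participating in the study", giving 16 scans per woman, eight on each device, in a blocked order prepared beforehand. The synopsis adds, in its description of the sessions: "The users will be instructed to take as many measurements as possible during the allotted time".
- **What a reading is.** From the synopsis: "Users will be instructed to use the VScan Access R2 device to take a 3 second video of the volunteer". From Section 5.7: "Each paired scan will last approximately 5 minutes for both determinations".
- **Who sees and records what.** Section 3.3 describes a "single-site, non-blinded, research study". Under Section 5.7, "eligible subjects will be fitted with a conventional FHR Monitor while simultaneously undergoing a non-invasive abdominal ultrasound scan". Section 6.6 states: "The operator will record FHR values estimated from the reference and research ultrasound devices to the CRF".
- **Bias control.** Section 1.3 names one measure, consecutive enrolment of eligible women.
- **Analysis.** No hypothesis is tested and summaries are descriptive (Sections 10.6 to 10.8). Missing data are not imputed (Section 10.9). The synopsis leaves the accuracy procedure to be finalised from Part 1.

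**The concern.** In a method comparison, the recorded pairs must represent what the device delivers. Here the operator may be able to see the reference while deciding whether to accept a Vscan reading, and a repeat takes seconds. If a discordant reading is repeated and only the second value reaches the CRF, eight complete pairs remain and agreement looks better than it was at the first attempt. If acquisitions that return no value are not counted, the results also hide how often the device fails to read.

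The harm would be an over-favourable accuracy description, not a false test result. That description is still the study's main product, and Section 12.6.1 lets the sponsor use the de-identified data for regulatory claims and marketing. Later analysis could not recover attempts that were never logged.

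**Working it through.** **1. The plan's own figures.** 8 pairs × 2 devices = 16 scans and 8 × 5 min = 40 min, as Section 5.7 states. One clip is 3 s / 300 s = 1% of a pair's slot. Positioning the probe and taking the reference use much of the rest, but a second clip would fit. Part 2 yields 96 pairs (synopsis: 4 sessions × 3 women = 12; × 8), 120 (Table 1: 15 women) or 160 (Section 10.7: 20 women).

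**2. What existing records would show.**

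| Provision | What it would reveal |
|---|---|
| Blocked schedule (5.7) | Order by operator and woman; not repeats |
| Information on when and how the exam was done (5.7) | Possibly timing; no attempt-level content required |
| Saved images (6.7) | Repeats, if every clip is kept; that is not required |
| Scan duration on the CRF (6.7) | A long session; not which reading was kept |
| Image-set count (10.8) | A total; not matched to attempts |
| Device deficiencies (8.7, 8.10) | Some failed readings, if classed as deficiencies |
| Source checks and monitoring (11.6.1, 11.6.3, 12) | CRF against source; no attempt log exists to check |

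Each helps in part. None is a log of attempts, and none sets the order in which the two values are fixed.

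**3. Illustration of size.** Every error figure here is assumed. Limits of agreement are used only as a familiar scale; the plan does not specify them.

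Let d be Vscan minus reference, distributed 0.9·N(0, 3²) + 0.1·N(0, 20²). Half of the readings with |d| > 10 bpm are affected.

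- Every first reading kept: variance 0.9×9 + 0.1×400 = 48.1; limits 1.96×√48.1 = ±13.6.
- For a component with SD s and a = 10/s, the probability outside ±10 is 2[1−Φ(a)], and its variance contribution is s²{2[1−Φ(a)] + 2aφ(a)}. Weighted over both components: P(|d|>10) = 0.0625, variance from outside 38.856, from inside 48.1 − 38.856 = 9.244.
- One independent repeat replaces the reading: 9.244 + 0.5×38.856 + 0.5×0.0625×48.1 = 30.2; limits ±10.8. Share within ±10 bpm: 0.9375 + 0.03125×0.9375 = 0.967, up from 0.938. No pair is missing.
- Gross errors persist on repeat: 28.672 + 0.5×(0.00077×9 + 0.0617×400) = 41.0; limits ±12.6.
- Pair left out instead: 28.672/0.9688 = 29.6; limits ±10.7. About 3.1% of pairs are missing (0.0312×96 = 3.0; ×120 = 3.7; ×160 = 5.0), visible as women with seven of eight.

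Other inputs, with the same half repeated once:

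| Gross-error share, SD | First readings | After repeats |
|---|---|---|
| 0% | ±5.88 | ±5.86 |
| 5%, SD 20 | ±10.5 | ±8.6 |
| 10%, SD 10 | ±8.3 | ±7.4 (±7.8 if persistent) |
| 20%, SD 20 | ±18.3 | ±14.4 |

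**4. Failed readings.** If 5% to 20% of attempts gave no value (assumed) and 95% of recorded readings lay within 10 bpm (assumed), the share of all attempts would be 0.95×0.95 = 90% down to 0.95×0.80 = 76%.

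**The case against.** The strongest reply is that the plan already limits repeats. The synopsis and Section 5.7 both say eight research scans. If each 3-second acquisition is a scan, a repeat is a ninth, and Section 9.8 would make it a protocol deviation to be reported or documented. Section 6.6 also gives no exception to recording, so discarding a value already obtained arguably departs from it. This stands, and it defeats a stronger reading that a reader might infer: that a repeat breaks no written rule. The documents do not support that. They leave the matter unclear, because 'scan' is not tied to the clip and a 5-minute pair could be read as holding more than one.

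A reader might also infer a flat contradiction between eight scans and as many measurements as possible. That goes too far. The phrase sits in the description of 3-4 hour sessions and can mean completing as many of the eight as time allows. It is an ambiguity.

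Three further points have weight. No section says the operator sees the reference first; this is inferred from non-blinding, simultaneous monitoring and one operator recording both values. It is most plausible where the monitor is the reference (Section 3.3) and less so for M-mode (Section 2.3). The Vscan value is semi-automated, so it cannot be shaded, only selected. And the accuracy procedure is still to be finalised from Part 1, although nothing promises that this will cover repeats or logging.

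Finally, the first returned value is not the only sensible target: accuracy after an ordinary quality-driven repeat is another. That bears on the choice of primary sample, not on the need for a log.

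**Conclusion.** The point holds as a gap in procedure that should be closed before Part 2. The order of fixing the two values and the logging of attempts are both unspecified, and the partial records would not reliably show selective repeats or failures. In the scenarios worked through, apparent agreement improves or hardly changes.

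It does not follow that the accuracy results will be inflated. The documents give no error SD, gross-error rate, failure rate or agreement limit, so the size cannot be derived and may be nil. The illustration rests entirely on the assumed error mixture, the 10 bpm trigger and half of the discordant readings being affected. Across those inputs the effect runs from essentially none (±5.88 to ±5.86 bpm) to several bpm (±18.3 to ±14.4). The CRF is not among the documents and may hold more fields than the protocol text requires.

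**What to change.** Make these changes when the accuracy procedure is finalised, before Part 2.

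1. Save the Vscan value before the reference value is viewed, or take the monitor value afterwards from a time-stamped record, if the monitor produces one (the documents do not say).
2. Log every Vscan attempt: number, time, operator, and value or 'no reading'.
3. Reconcile the log with the saved clips.
4. Report the proportion of attempts that gave a reading alongside agreement.
5. Define 'scan' in relation to the 3-second clip and reconcile the synopsis wording with Section 5.7.
6. State in advance which acquisition is the primary sample, and also show agreement over all logged readings.

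Items 1 to 4 reduce the bias or make it visible; items 5 and 6 remove the ambiguity. The cost is one CRF line per attempt and a fixed order of saving values, with no extra staff where the monitor is the reference. Headline accuracy may come out slightly lower.
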